		2nd	Upon improvement to Grade ≤2. GCSF support may be used.	If improved within 7 days, dose reduce by one level. If no improvement within 7 days, permanently discontinue drug.
		3rd	Permanently discontinue study drug.	
Thrombocytopenia	Grade 4 (platelet count <25,000/mm3)	1st	Upon improvement to Grade ≤2 (platelet count >50,000/mm3) within 14 days	If improved within 14 days, continue same dose. If no improvement within 7 days, permanently discontinue drug.
		2nd	Upon improvement to Grade ≤2 (platelet count >50,000/mm3) within 14 days	If improved within 14 days, dose reduce by one level. If no improvement within 7 days, permanently discontinue drug.
		3rd	Permanently discontinue study drug.	
Other non-hematologic	Grade 3 adverse events	1st	Hold until improved to Grade ≤1	If improved within 5 days, continue same dose. If >5 days, dose reduce by one level.
		2nd	Hold until improved to Grade ≤1.	If improved within 5 days, dose reduce by one

				level. If >5 days, permanently discontinue.
Other non-hematologic	Grade 4 adverse events	1st	Permanently discontinue study drug	

Treatment Plan

Investigational product

PLX51107 will be supplied by Plexxikon in 20 mg tablet formulations. Each participating site must have sufficient supply for one cycle (28 days) available prior to enrollment of each patient. Additional months' supplies will be ordered by the site accordingly.

All patients will receive prednisone 1-2 mg/kg orally daily (may be divided into 2 doses) or MP IV equivalent. Corticosteroids may be tapered per institutional guidelines but initiated no sooner than 7 days after Study Day 1 and to no less than prednisone 0.25mg/kg daily before Study Day 28. The minimum dose of prednisone at Study Day 1 is 1mg/kg (or MP IV equivalent).

Treatment Dosage and Administration

The first day of administration is deemed Study Day 1. The dosage administered is determined by dose level in Table 1 and in observance of DLT or SAE considerations.

Treatment will be administered orally daily. The first day of administration is Study Day 1. PLX51107 should be taken at approximately the same time of day. On Study Days 1, 8, and 15 when PK/PD sample collections are drawn, patients should fast 8 hours prior and 1 hour after daily dose administration. On other days when, there are no scheduled PK/PD sample collections, patients should fast 2 hours prior and 1 hour after daily dose administration.

Dosing Delays or Missed Doses

Doses delayed by more than 2 hours should be skipped. Doses obscured by vomiting should not be re-administered. If more than 7 doses of the first 28 are missed due to noncompliance, the patient will be considered invaluable and study subject replaced. Patients with missed doses removed from evaluation will continue to be monitored for safety.

Duration of Therapy

Dosing is continued until

- 6 months from initiation of study drug. If dose is greater than 20 mg at 6 months, drug should be tapered over maximum one additional month for a maximum of 7 months.
- CR is reached with daily prednisone equivalent \leq 10mg/day. If CR is reached within <6 months, study drug is then tapered by 20 mg over one month.
- toxicity
- relapse of underlying malignancy
- progression of GVHD
- lack of response as defined by No Response in any organ system by Study Day 28
- voluntary withdrawal from study

Duration of Follow-Up

All patients will be followed for up to 6 months from initiation of study drug or 30 days from drug discontinuation (end of treatment, aka EOT) whichever is longer except in the cases of voluntary withdrawal from study or death.

For subjects who withdraw consent, there must be clear documentation of whether the subject withdraws consents to treatment only (i.e. agrees to follow-up) or withdraws consent to treatment and follow-up.

Follow-up

Follow-up appointments will entail review of concomitant medications, physical exam with vital signs, assessment of ECOG performance status, adverse event evaluation, GVHD staging, and assessment for relapse/survival. Labs will also be collected for complete blood count (CBC), comprehensive metabolic panel (CMP), coagulation labs (PT, aPTT, INR). Peripheral blood for PK, PD, ELISA, and immune reconstitution will be collected as above in the Study Calendar and in the Correlative Studies section (below). Patients will be followed weekly for the first two cycles of study drug and monthly thereafter until study drug discontinuation. Additional evaluations will occur at time of SAE or DLT, scheduled 6-month follow-up from initiation of study drug, and end of treatment (30 days from drug discontinuation). All follow-up will be done in-person with the exception of Cycle 2 Days 8, 15, and 22, which may optionally be done via secure video, per the physician's discretion.

Concomitant medications

Of the 5 major CYP isoforms, 3A4 and 2C8 may be involved in Phase I metabolism of PLX51107, with possibly CYP2B6 and CYP2D6 playing a minor role. Until information regarding exposure-toxicity and exposure-response relationships are available with PLX51107, concomitant CYP3A4 and CYP2C8 inhibitors and/or inducers should be administered with caution in the event they alter the systemic exposure to PLX51107 (see Appendix for a list of strong CYP3A4/2C8 inhibitors and inducers). In general, strong inhibitors or inducers of CYP3A4 and CYP2C8 should be avoided unless absolutely necessary. These include anticonvulsants (phenytoin, carbamazepine, phenobarbital), mycin antimicrobials, azole antifungals and anti-retrovirals. Strong CYP3A4 and CYP2C8 inducers or inhibitors should be discontinued at least 14 days or 5 drug half-lives, whichever is longer, prior to the initiation of dosing with PLX51107, unless there is no alternative and the medication is absolutely necessary.

Should treatment with a strong CYP3A4 or strong CYP2C8 modulator be necessary, study drug should be discontinued during this time, and for at least 14 days or 5 drug half-lives afterwards, whichever is longer.

Concomitant medications are recommended as prophylaxis for nausea, vomiting, and infections, and are allowed for managing myelosuppression.

Initiation of QTc prolonging drugs should be performed with caution. QTc should be monitored closely with any new initiation or dose adjustment. Electrolytes should be monitored and repeated.

The concurrent use of systemic immunosuppressants commonly used for GVHD prophylaxis (calcineurin inhibition (tacrolimus, cyclosporine), mycophenolate, mofetil, and sirolimus) may enhance the immunosuppressant effects of PLX51107. Because the interactive effects of these drugs with PLX51107 are as yet unknown, proceed with caution and monitor drug

levels (tacrolimus cyclosporine, sirolimus) at minimum twice weekly and dose adjust as necessary to desired concentration

Steroids may be tapered based on starting steroid dose according to the below recommended schedule or per institutional guidelines:

% of Starting dose	Steroid Dose	Days	Number of days	% Decrease from previous dose
100%	1 mg/kg/day	Days 1-7	7	
75%	0.75 mg/kg/day	Days 8-14	7	25%
50%	0.5 mg/kg/day	Days 15-21	7	33%
25%	0.25 mg/kg/day	Days 22-28	7	50%
10%	0.2 mg/kg/day	Day \geq 29 and onwards		20%

% of Starting dose	Steroid Dose	Days	Number of days	% Decrease from previous dose
100%	2 mg/kg/day	Days 1-7	7	
75%	1.5 mg/kg/day	Days 8-14	7	25%
50%	1 mg/kg/day	Days 15-21	7	33%
25%	0.5 mg/kg/day	Days 22-28	7	50%
13%	0.25 mg/kg/day	Days 28-35	7	50%
10%	0.2 mg/kg/day	Day \geq 36 and onwards		20%

Preparation, Reconstitution, and Dispensation

PLX51107 is an anticancer drug and, as with other potential toxic compounds, caution should be exercised when handling PLX51107.

Study Drug Packaging and Labeling

PLX51107 tablets are manufactured, packaged, and labeled according to current Good Manufacturing Practice (cGMP) at the following address:

BioDuro LLC (Formerly known as Formex LLC)
[name]
[name]

Storage and Handling

[figure not shown]
PLX51107 tablets should be stored at room temperature 20°C to 25°C (68°F–77°F); excursions permitted between 15°C and 30°C (59°F and 86°F). Subjects will be requested to store the study drug at the recommended storage conditions noted on the label.

The study drug provided in accordance with this protocol will be kept in a secure place and will only be supplied to subjects participating in this study. The Principal Investigator is accountable for all study drug in accordance with this protocol. In addition, the Principal Investigator must keep accurate and up-to-date dispensation records. Any study drug accidentally or deliberately destroyed must be recorded in a timely fashion, including an explanation for the destruction in writing. Any discrepancies between the amounts of study drug dispensed and returned must also be explained in writing.

All unused and partially used study drug must be sealed and returned to the Sponsor or designee, or destroyed on site in accordance with the established procedures for drug destruction. Details of destruction, including, but not limited to, the number of boxes destroyed, batch number, and the date and method of destruction must be recorded on the study drug destruction logs.

Correlative Studies

Plasma will be collected for PK on Cycle 1 Days 1, 8, and 15 and assessed pre-dose and at hours 1, 3, 5, and 7 post-dose on Days 1 and 8 and pre-dose and at 3 hours post-dose on Day 15. PD for markers of BRD4 target engagement will also be collected on Days 1 and 8 (pre-dose and 3 hours post-dose). Notably, despite the short half-life of PLX51107, pre-clinical studies have shown that BRD4 target engagement persists despite drug metabolism (Figure 4).⁹ A separate PK and PD for GI GVHD patients will be sub-analyzed given possible malabsorption complications of this oral drug. Additional samples for PK and PD (with pre-dose and 3 hours post-dose times) may be collected if a subject experiences a DLT, serious adverse event (SAE), AE of special interest, dose modification, or at the PI's request.

Whole blood samples for immune reconstitution analyses by flow cytometry and epigenetic markers by mass cytometry will be collected on all patients from start of treatment and then weekly thereafter for 4 weeks total and monthly for up to 6 months after initiation and at time of an SAE, DLT, and end of treatment.

Serum samples for GVHD biomarkers for Ann Arbor risk stratification (ST2 and REG3α ELISA) will be collected at time of study enrollment and weekly for four weeks after treatment initiation⁴⁸. Ann Arbor scores will be correlated with response to therapy and NRM⁴⁸.

Study procedure and methods

Screening

Patients who meet eligibility criteria and consent will begin treatment (Study Day 1) with PLX51107 per the designated dose level. Those who are ineligible per criteria are deemed screen failures and logged as such.

SR-aGVHD Dx

Follow-up

Due to the studied disease characteristics, patients are anticipated to be hospitalized initially, during which time close assessments may be made as standard of care. However, at a minimum, patients must be assessed weekly for GVHD or toxicity throughout study drug treatment.

Withdrawal

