To assess the safety and tolerability, adverse events by grade will be summarized. The occurrence of Grade 3+ adverse events according to CTCAE will be summarized as well. Adverse events will initially be reviewed regardless of attribution, but also according to whether adverse events are possibly, probably, or definitely related to treatment. Complete response (CR) at Day 28 among all patients treated and among all patients treated at BETD will be estimated. The proportion of CR with a 95% CI will be reported, assuming a binomial distribution. The overall response rate (ORR) will include CR and partial response (PR), while mixed response (MR) and no response (NR) will be classified as no response. The ORR will be similarly analyzed as CR. To determine 6-month non-relapse mortality (NRM), the event will be death due to reasons other than disease and the time will be measured from the date of starting PLX51107 to date of death with the competing risk as death due to disease (relapse). The cumulative incidence curve accounting for competing risks will be generated to estimate the cumulative incidence of NRM rate at 6 months. The comparison in NRM between patient subgroups may be explored graphically.

Study endpoints

The primary endpoints include:

- To determine the biologically effective and tolerable dose (BETD)
- Safety endpoints (adverse events)
- PK analysis

The secondary endpoints include:

- Preliminary efficacy (CR at Day 28) among all patients treated and among all patients treated at BETD
- Overall response rate (ORR at Day 28) among all patients treated and among all patients treated at BETD
- NRM at 6 months

GVHD Response Definitions

Acute GVHD response will be in comparison to the acute GVHD staging upon Screening. The Mount Sinai Acute GVHD International Consortium (MAGIC) criteria¹⁴ will be used to assess staging and grading. Response will be defined as below (as previously used in BMT-CTN 1802 clinical trial: https://web.emmes.com/study/bmt2/protocol/1802_protocol/1802_protocol.html)

Complete Response (CR) is defined as complete resolution of all signs and symptoms of acute GVHD equivalent to staging 0 in all organs.

Partial Response (PR) is defined as improvement in one or more organs involved at diagnosis/screening and without progression or new acute GVHD symptoms in any organ.

Mixed Response (MR) is defined as improvement in one or more organs involved at diagnosis/screening but with progression or new symptoms in any organ.

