No Response (NR) is defined as no improvement and/or progression of acute GVHD symptoms in any organ.

Number of Subjects

The minimum number of patients accrued to the Phase 1 portion is 6 patients (3 patients with ≥ 2 DLTs at Dose Levels 1 and 0) with maximum of 18 patients (6 patients each at Dose Levels 1-3).

Duration

We anticipate a screen failure rate of approximately 40% and enrolling a maximum 18 patients. The expected time to screen 45 patients at our center would span approximately 2 years. Patients will require at least 6 months of follow-up (6 months after initiation of study drug or 30 days after discontinuation of study drug). Total duration of this trial is expected to take approximately 2.5 years.

Study Calendar

	Cycle 1				Cycle 2				†Cycle 3+	SAE/DLT	*6-mo F/U	EOT	
	Screening	Day 1	Day 8	Day 15	Day 22 ±3	Day 1	Day 8 ±3	Day 15 ±3	Day 22 ±3	Day 1 ±3	±3 days	±7 days	±7 days
Informed Consent/Eligibility Review	X												
Concomitant Medication Review	X		X	X	X	X	X	X	X	X	X	X	X
Physical Exam with Vital Signs	X		X	X	X	X	X	X	X	X	X	X	X
ECOG Performance Status	X		X	X	X	X	X	X	X	X	X	X	X
PLX51107		Daily											
Adverse Event Evaluations		X	X	X	X	X	X	X	X	X	X	X	X
Complete Blood Count (CBC)	X		X	X	X	X	X	X	X	X	X	X	X
Comprehensive Metabolic Panel (CMP)	X		X	X	X	X	X	X	X	X	X	X	X
PT/aPTT/INR	X		X	X	X	X	X	X	X	X	X	X	X
Serum Pregnancy Test	X												
GVHD Staging	X		X	X	X	X	X	X	X	X	X	X	X
Relapse, Survival			X	X	X	X	X	X	X	X	X	X	X
Peripheral Blood for PK		X	X	X									
Peripheral Blood for PD		X	X								X		
†Peripheral Blood for MAP		X	X	X	X	X							
Peripheral Blood for Immune Reconstitution		X	X	X	X	X				X	X	X	X

†Applies to C3D1, C4D1, C5D1, and C6D1

*6 month follow-up may overlap with EOT. In this case, these will be deemed EOT days.

‡MAP refers to MAGIC Algorithm Probability

Please note: $C_n D_{28} = C(n+1)D_1$

Dose limiting toxicity (DLT)

DLTs are defined as AEs or laboratory abnormalities occurring during the first cycle (28 days) of study drug administration that are at least possibly related to PLX51107, deemed to be clearly unrelated to disease progression, concurrent illness or concomitant medication and that meet one of the following NCI CTCAE v5.0 criteria below.

- **Hematological toxicities**
 - Grade >3 neutropenia lasting >7 days
 - Grade ≥ 3 febrile neutropenia
 - Grade 4 thrombocytopenia lasting >14 days despite study drug discontinuation
- **Non-hematological toxicities**

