In an acute GVHD patient population with no concern or evidence of active disease or suspicion of relapse, there is no known basis for the development of differentiation syndrome. Subjects with active disease/relapse are excluded from enrolling (exclusion criterion 3), and all enrolled subjects undergo a weekly physical examination with vital sign assessment and laboratory monitoring. In the event that an enrolled patient develops relapse of disease, PLX51107 must be discontinued immediately and the patient withdrawn from study.

Adverse Events and Adverse Event Management

Safety and tolerability will be monitored and determined by serial physical examinations, vital signs, hematology and chemistry laboratory studies, and reported AEs (including deaths and other SAEs and treatment-emergent AEs). The Investigator will monitor the laboratory test findings. If any laboratory test is abnormal during the course of the study, it will be followed at the discretion of the Investigator. Abnormalities of laboratory tests are evaluated by the Investigator and assessed as either clinically significant or not clinically significant. Abnormal laboratory values deemed by the Investigator to be clinically significant and, thus, constitute or are associated with an AE, must be reported on the AE form. Abnormal laboratory values that require intervention must be reported on the AE form whether or not deemed clinically significant.

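### 6-month NRM is defined by cause of death with disease death, not relapse, as the competing event, so the estimate depends on unsettled post-relapse follow-up and on how later deaths are attributed

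*Combined protocol and SAP*

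**What the plan says.** The Statistical analysis plan, repeated in the Data analysis row of the Synopsis, states that for NRM "the event will be death due to reasons other than disease". Time runs from first PLX51107 dose to death, "with the competing risk as death due to disease (relapse"). The estimator is a cumulative incidence curve at 6 months that accounts for competing risks.

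Four places bear on what is observed after relapse:

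- **Differentiation Syndrome:** if a patient relapses, "PLX51107 must be discontinued immediately and the patient withdrawn from study".
- **Duration of Therapy:** relapse of the malignancy is listed as a reason to stop dosing.
- **Duration of Follow-Up:** all patients are followed to 6 months from first dose or 30 days after stopping, "whichever is longer except in the cases of voluntary withdrawal from study or death".
- **Duration** (under Number of Subjects): "Patients will require at least 6 months of follow-up".

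NRM at 6 months is one of three listed secondary endpoints. Correlative Studies also uses it: "Ann Arbor scores will be correlated with response to therapy and NRM". The section on potential benefits names improved NRM as the hoped-for gain.

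**The concern.** NRM is conventionally death without prior relapse, with relapse as the competing event on the day it occurs. A patient's contribution is then fixed at relapse. Here the bracketed word relapse only labels a kind of death: the clock runs to death and the competing event is a death. Two things after relapse therefore enter the estimate.

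The first is follow-up. If relapsed patients leave the study and are censored, the analysis treats them as having the same later NRM hazard as relapse-free patients. If every disease death is preceded by a recorded relapse, no disease death would then be observed at all, and the competing-risks curve would reduce to one minus Kaplan-Meier.

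The second is attribution. If relapsed patients are followed, each later death must be classed as disease or non-disease. These patients have refractory GVHD and are on steroids, so GVHD, infection and malignancy can all be plausible causes. The available text gives no rule for assigning cause.

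Two analysts could report different NRM from the same patients, each following the plan.

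**Working it through.** The plan states no expected NRM or precision, so there is no figure to reproduce. The check has three parts.

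**1. The follow-up statements side by side.** Duration of Follow-Up excepts only voluntary withdrawal and death. Withdrawal required by the protocol at relapse is neither, so that section keeps relapsed patients under observation. The Differentiation Syndrome text takes them off study. The 6-month minimum under Duration does not decide the matter, because its parenthesis offers 6 months after starting or 30 days after stopping without saying which governs.

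**2. Constant-hazard model.** Inputs, all assumed:

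- Net 6-month NRM (the risk if relapse could not occur) of 48% or 30%. Background & Significance gives 48% NRM for steroid non-responders, but with no time horizon.
- Net 6-month relapse of 10%, 20% or 30%.
- Median relapse-to-death time m of 2 or 4 months.
- A fraction f of post-relapse deaths called non-disease.

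With 6 months as one time unit, the hazards are l = −ln(1 − NRM), r = −ln(1 − relapse) and d = ln 2/(m/6).

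- Death without relapse: C = l/(l + r) × (1 − e^−(l + r)).
- Relapsed patients censored: 1 − e^−l, which is the net NRM.
- Relapsed patients followed: C + f·p, where p = ∫₀¹ r·e^−(l + r)t·(1 − e^−d(1 − t)) dt is the probability of relapse and then death within 6 months.

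Worked case, NRM 48% and relapse 20%: l = 0.6539, r = 0.2231, so C = 0.7456 × 0.5840 = 0.435. Censoring gives 0.480, an excess of 4.5 points.

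| Net NRM | Net relapse | C | Excess if censored | Excess if followed, f = 0.3 (m = 2 / m = 4) |
|---|---|---|---|---|
| 48% | 10% | 45.8% | 2.2 | 1.4 / 0.9 |
| 48% | 20% | 43.5% | 4.5 | 2.8 / 1.9 |
| 48% | 30% | 41.2% | 6.8 | 4.3 / 2.9 |
| 30% | 10% | 28.6% | 1.4 | 1.5 / 1.0 |
| 30% | 20% | 27.1% | 2.9 | 3.1 / 2.1 |
| 30% | 30% | 25.5% | 4.5 | 4.8 / 3.2 |

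Excesses are in percentage points over C. With f = 0 the excess under follow-up is zero.

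Against the SAP's literal cause-of-death definition, full follow-up is unbiased and censoring can err either way. It overstates NRM when f is below (net NRM − C)/p and understates it above. That break-even is about 47% (m = 2) or 71% (m = 4) at net NRM 48%, and about 28% or 42% at net NRM 30%.

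**3. Illustrative 18 patients.** Deaths without relapse at months 0.8, 1.2, 1.7, 3.1, 4.0 and 5.2; relapses at 2.0, 2.3 and 2.6; nine others alive at month 6.

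- Relapse as competing event: 6/18 = 33.3%.
- Censored at relapse: three deaths among 18, then three among the 12 still at risk: 3/18 + (15/18)(3/12) = 37.5%.
- Followed, all three die of disease: 6/18 = 33.3%.
- Followed, all three die, one death called non-disease: 7/18 = 38.9%.

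The exact (Clopper-Pearson) 95% interval for 6/18 is 13.3% to 59.0%.

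**The case against.** There are four good points on the other side.

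First, the follow-up texts can be read together. Follow-up excepts only voluntary withdrawal and death, the calendar schedules relapse and survival at the 6-month and end-of-treatment visits, and the off-study sentence sits in a safety discussion that says nothing about censoring. The text under the Withdrawal heading, not in the copy reviewed, may confirm this. If so, the censoring figures fall away. This stands as a possible reading. It does not remove the disagreement between the two sections as worded, and it leaves attribution open.

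Second, cause-specific mortality with a competing-risks estimator is a coherent estimand, so preferring death without prior relapse changes the estimand rather than corrects an algebraic error. That is true. But the cause-of-death version needs assured post-relapse follow-up and an attribution rule, and the available text secures neither.

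Third, the sizes rest wholly on assumptions: the relapse rate, the time from relapse to death and the 30% attribution fraction have no source in the documents. That also stands; the ranges show sensitivity and predict nothing.

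Fourth, the excess is small beside an interval about 46 points wide, and no decision rule uses NRM. Both are correct and limit the weight of the point. They do not excuse an endpoint that can take different values in the same patients: with 18 patients, reclassifying one death moves the estimate by 1/18 = 5.6 points.

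**Conclusion.** The concern holds. As written, the 6-month NRM estimate depends on what happens after relapse. Two protocol sections disagree on whether that is observed, and the available text gives no rule for classifying the deaths.

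Over the assumed range (net NRM 30% to 48%, net relapse 10% to 30%), censoring at relapse lifts the estimate 1.4 to 6.8 points above death without prior relapse. Full follow-up lifts it by zero if every post-relapse death is called disease, and by 0.9 to 4.8 points if 30% are called something else.

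This affects a secondary endpoint and the biomarker correlation that uses it. It does not affect the choice of the biologically effective and tolerable dose. It should be fixed because the repair is easy, not because the likely distortion is large.

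**What to change.** In the Statistical analysis plan and the Synopsis:

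- Define NRM as death without prior relapse or progression of the underlying malignancy, timed from first PLX51107 dose.
- Make relapse or progression the competing event, at its own date.
- Censor patients who are alive and relapse-free at last contact.
- Estimate 6-month NRM by Aalen-Johansen cumulative incidence.
- List observed post-relapse deaths separately, with cause.

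Reconcile Duration of Follow-Up with the Differentiation Syndrome text on whether patients are followed after relapse. If the cause-of-death definition is kept instead, the plan needs explicit survival follow-up after relapse and a written attribution rule.

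The cost is about two sentences in the SAP and Synopsis and one in the protocol. Relapse and survival are already on the Study Calendar, so no new assessment is needed. The downside is that non-disease deaths after relapse leave the NRM figure and appear only in the listing.

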Subsite patients will have eligibility verified and will be entered on study centrally at The Ohio State University by the Multi-Center Trial Program (MCTP). All subsites must email the MCTP to verify slot availabilities prior to consenting patients. Once a patient signs consent, the signed consent document and documentation of the consenting process must be faxed or securely emailed to the MCTP. The required forms, including Eligibility Criteria Checklist and Registration Form, can be found in the Supplemental Forms Document.

To register a subsite patient, the following documents must be completed by the subsite research team and faxed or securely e-mailed to the MCTP:

- Copy of all baseline tests required per the protocol calendar. Tests must be within the specified window.
- Signed Patient Consent Form, if not previously sent
- Signed Patient HIPAA Authorization Form (if separate), if not previously sent
- Consent Documentation Note, if not previously sent
- Completed & Signed Eligibility Checklist (refer to Supplemental Forms Document)
- Registration Form (refer to Supplemental Forms Document)
- Source documents verifying every inclusion & exclusion criteria

Upon receipt of registration documents, the MCTP will send an email confirming receipt. If confirmation of receipt is not received within 24 hours of submission, please contact the MCTP by phone and/or pager to confirm receipt.

Upon receipt of all required registration documents and upon verification the subsite patient meets all eligibility criteria, the MCTP will:

- Assign the patient a study sequence ID, if not already provided at time of consent
- Register the patient on the study
- Fax and/or e-mail the subsite the completed Registration Form with the assigned study sequence ID and registration date as confirmation of patient registration

Following registration, patients should begin protocol treatment within **5** business days. Issues that would cause treatment delays should be discussed with the Principal Investigator and MCTP as soon as possible. If a patient does not receive protocol therapy following registration, the PI and MCTP must be notified immediately within 1 business day.

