Each participating institution will order study agents directly. Agents may be ordered by a participating site only after the required regulatory documents, including the initial IRB approval for the site, have been forwarded to the MCTP and all other study-specific requirements have been met (as outlined during site activation).

Inclusion criteria

1. Age \geq 18 years
2. Treatment-refractory acute GVHD as defined as patients who failed steroids (as defined as (a) progressed after 3 days of treatment with methylprednisolone (MP) 2 mg/kg/day equivalent, (b) did not improve after 7 days of treatment with MP 2 mg/kg/day equivalent, (c) progressed to a new organ after treatment with MP 1 mg/kg/day equivalent for skin and upper gastrointestinal (GI) GVHD, or (d) recurred during or after a steroid taper²) plus one or more salvage regimens with no limit to the number of prior lines of salvage therapies
3. Recipients of ablative and reduced-intensity conditioning regimens
4. Recipients of HLA-matched related and unrelated, 1-allele mismatched, haploidentical, or umbilical cord blood donor grafts
5. Prior lines of therapy for treatment of steroid-refractory acute GVHD are allowed. There is no minimum or maximum to the number of prior therapies. However, exposure to investigational therapies for the treatment of GVHD must be $>$ 14 days or 5 half-lives (whichever is longer) of first administration of study drug. Prior cell therapy trial exposure must be $>$ 14 days where no known half-life applies. For patients treated with ruxolitinib for the treatment of acute GVHD, ruxolitinib must be discontinued by at least one day prior to initiation of PLX51107.
6. ECOG performance status 0-3
7. Absolute neutrophil count $\geq 1.0 \times 10^9/L$ for 3 consecutive days). Use of growth factor support is allowed.
8. Platelet count $\geq 50 \times 10^9/L$ without transfusion support for 2 consecutive days.
9. Women of child-bearing potential must have a negative serum pregnancy test at Screening and must agree to use an effective form of contraception from the time of the negative pregnancy test up to 6 months after the last dose of study drug. Effective forms of contraception include abstinence, hormonal contraceptive in conjunction with a barrier method, or a double barrier method. Women of non-child-bearing potential may be included if they are either surgically sterile or have been postmenopausal for ≥ 1 year.

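### GVHD response is compared with Screening staging and none is scheduled on Day 1, so a change in stage before the first dose can enter the Day 28 overall response rate

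*Combined protocol and SAP*

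**What the plan says.** All places are in the combined protocol and SAP.

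- **Comparator.** GVHD Response Definitions opens with "Acute GVHD response will be in comparison to the acute GVHD staging upon Screening".
- **Partial response (PR).** It is "improvement in one or more organs involved at diagnosis/screening and without progression or new acute GVHD symptoms in any organ". Mixed response (MR) uses the same reference to diagnosis/screening.
- **No response (NR).** "No Response (NR) is defined as no improvement and/or progression of acute GVHD symptoms in any organ". The definition names no reference time of its own.
- **Complete response (CR).** It is "complete resolution of all signs and symptoms of acute GVHD equivalent to staging 0 in all organs", which is a state on the day and not a change from baseline.
- **Staging visits.** The GVHD staging row of the Study Calendar is marked at Screening, blank at Cycle 1 Day 1, and marked at Day 8 and every later visit.
- **Time to first dose.** Subject Registration Procedures: "Following registration, patients should begin protocol treatment within 5 business days".
- **Treatment before first dose.** Inclusion criterion 5: "ruxolitinib must be discontinued by at least one day prior to initiation of PLX51107".
- **Use of the response classes.** Day 28 ORR (CR plus PR) is a secondary endpoint. Study Design says that clinical responses are among the items reviewed to justify the RP2D. Duration of Therapy uses the No Response class at Study Day 28 as one of the reasons for ending dosing.

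**The concern.** A response rate for a new drug should measure change from the patient's condition when the drug was started. Here the reference is an earlier assessment, and nothing scheduled records the GVHD stage at first dose. If a patient improves between Screening and Day 1 and merely holds that improvement, the plan can class the patient as PR. If a patient worsens in that interval and then recovers on PLX51107 only as far as the Screening stage, the plan shows no improvement. Both are misattributions, in opposite directions.

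At stake are the PR, MR and NR classes, the Day 28 ORR built from them, and the clinical response evidence in the RP2D review. A pre-dose stage that was never recorded cannot be reliably recovered later.

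**Working it through.** The plan gives no power, target rate or other figure that depends on the response baseline, so there is nothing to reproduce. The check sets the sections side by side and then sizes a single reclassification.

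**1. Is the blank Day 1 cell real?** The calendar has 13 visit columns and the GVHD staging row has 13 cells, the second of them blank. The PK row of the same table is marked at Days 1, 8 and 15, which agrees with the text of Correlative Studies. The columns have therefore not shifted. Elsewhere, Study procedure and methods requires weekly GVHD assessment during study drug treatment, which does not supply a pre-dose value. I found no rule that resets the baseline at first dose.

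**2. How long can the gap be?** Registration to first dose is at most 5 business days, which is 7 calendar days when a weekend falls inside it (5 + 2). Time from Screening to registration is added. The registration section refers to a specified test window, but I found no length for it, so this part cannot be sized. The minimum gap is zero, when Screening and first dose fall on the same day.

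**3. Can treatment change in the gap?** Yes, but it need not. Ruxolitinib must be off at least one day before PLX51107, so it can be stopped after Screening staging or before it. The minimum prednisone dose is specified at Study Day 1, not at Screening, so the steroid dose can also change in the interval.

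**4. Which outcomes depend on the baseline?**

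- PR, MR and NR depend on it, and hence ORR.
- CR is stage 0 in all organs. It does not depend on baseline, except for a patient who is already at stage 0 by Day 1.
- The BETD is decided on Day 1 AUC and DLTs and does not use response.
- NRM is timed from the start of PLX51107 and is not affected.

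**5. Size of one reclassification.** The denominators come from Number of Subjects: at most 18 in all (3 dose levels × 6) and 6 at a dose level. The change in ORR is 1/n.

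- n = 18: 1/18 = 5.6 points. For example, 6/18 = 33.3% (exact 95% CI 13.3 to 59.0) becomes 7/18 = 38.9% (17.3 to 64.3).
- n = 6: 1/6 = 16.7 points. For example, 2/6 = 33.3% (4.3 to 77.7) becomes 3/6 = 50.0% (11.8 to 88.2).

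**6. Illustration under assumed rates.** The documents give no rate of pre-dose change, so the values of p, q and r below are assumptions and not estimates. Let p be the true ORR.

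- If a share q of non-responders improved before the first dose and held it, apparent ORR = p + (1 − p)q. With p = 30% and q = 5%, 10% or 20%, this is 33.5%, 37% or 44%.
- If a share r of responders worsened before the first dose and only regained their Screening stage, apparent ORR = p(1 − r). With p = 30% and r = 5%, 10% or 20%, this is 28.5%, 27% or 24%.
- For p from 20% to 50%, the upward shift (1 − p)q runs from 0.50 × 0.05 = 2.5 points to 0.80 × 0.20 = 16 points. The downward shift pr runs from 0.20 × 0.05 = 1 point to 0.50 × 0.20 = 10 points.

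**The case against.** **The gap may be short.** The 5 business days are a ceiling. Patients are expected to be in hospital at first, and the screening text has eligible, consenting patients go on to Study Day 1. This stands: the documents show that pre-dose change can enter the response class, not that it does so in any given patient.

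**Ruxolitinib.** A reader might infer that ruxolitinib is withdrawn between Screening and Day 1. The criterion sets only the latest stopping time. Some patients may have stopped before Screening, and others may not be taking it.

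**Speed of change.** A reader might take the 3-day and 7-day intervals in the steroid-failure criteria as evidence that stage often moves this quickly. Those intervals define failure of a steroid course. They give no rate of stage change in already refractory patients awaiting a new drug.

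**Diagnosis as a second baseline.** A reader might infer that improvement since the original GVHD diagnosis, achieved on earlier therapy, counts as PR. The opening sentence of the same section fixes Screening as the comparator, and the diagnosis/screening phrase qualifies which organs were involved. It is ambiguous wording that should be tidied, not a rival baseline.

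**Little depends on it.** ORR is a descriptive secondary endpoint with no test, no ORR threshold is stated for the RP2D, and at 2/6 the exact interval already spans about 4% to 78%. Sampling error is indeed much larger than one reclassification. But imprecision is no reason to keep an avoidable attribution error.

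**Screening is used consistently.** Physical examination, ECOG, blood count and metabolic panel are also blank on Day 1. That shows a coherent calendar, but it does not make Screening the better reference for judging the drug's effect.

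**Conclusion.** The point holds as a cheap improvement. The plan's stated rule allows a change in GVHD stage between Screening and first dose to be credited to or charged against PLX51107 in PR, MR and NR, and so in Day 28 ORR. The direction can go either way. Each reclassified patient is worth 5.6 points at n = 18 and 16.7 points at n = 6, but the number of such patients cannot be derived from the documents, and it is zero wherever there is no change in stage before the first dose.

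The documents do not support reading this as a threat to the primary dose decision or to Day 28 CR, since neither depends on baseline staging beyond the stage-0 exception noted above. The conclusion assumes that the calendar is complete as read. A screening window stated elsewhere would limit the gap but would not add a Day 1 staging.

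**What to change.** 1. Add MAGIC staging before the dose on Cycle 1 Day 1 to the Study Calendar.
2. In GVHD Response Definitions, define baseline as the last staging before the first PLX51107 dose, with Screening staging used if Day 1 is missing.
3. Use that one baseline for PR, MR and NR, and replace the diagnosis/screening wording in PR and MR with baseline.
4. Keep Screening staging for eligibility.
5. Because Duration of Therapy uses the No Response class at Day 28, moving the baseline can change who falls in that class. The sponsor must reconcile that section with the revised definition. No change to the clinical rule is proposed here.

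The cost is one extra bedside staging at a visit that patients already attend for PK sampling from pre-dose to 7 hours, with any laboratory component taken from the most recent pre-dose result, plus the wording changes and the reconciliation in item 5.
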